6.4.2 Clinical Assessments During Study

Blood Pressure & Pulse: A CRU staff member will check and record blood pressure and pulse prior to, and then approximately 30 minutes following, each dose and prior to discharge.

Other Side Effects/Tolerability: Side effects and tolerability of the IN administration will be collected as self-reports by subjects during both part 1 and part 2.

Assessment of Safety: Safety assessments include adverse events during the 6-hour period of observation.

6.4.3 Drug Assay and Pharmacokinetic Analyses

A validated, liquid chromatography-mass spectroscopy assay will be used to measure naloxone concentrations.

Non-compartmental Pharmacokinetics Analysis: T_{max} and C_{max} will be determined from visual inspection of the naloxone concentration-time plots. Pharmacokinetic analysis will be performed with WinNonLin (Certara, Princeton, NJ, USA), a pharmacokinetic data

analysis package, and will include calculation of the area under the concentration-time curve (AUC) as well as other parameters as detailed below. Descriptive statistics will be used to summarize the data from this study. Descriptive statistics will include numbers of subjects (n), mean, median, standard deviation (SD), minimum, and maximum for continuous data and frequencies and percentages for categorical data. For each subject, the following pharmacokinetic parameters will be determined:

- C_{max}: maximum observed plasma concentration
- T_{max}: time to C_{max}
- AUC_{0-t}: area under the plasma concentration-versus-time curve from time zero to the last sampling time at which concentrations were at or above the limit of quantification, calculated by the linear trapezoidal rule
- AUC_{0-12hr}: area under the plasma concentration-versus-time curve from time zero to 12 hours post-dose
- AUC_{0- ∞}; area under the plasma concentration-versus-time curve from time zero to infinity, calculated from AUC_{0-t} + (Ct/ λz), where Ct is the last observed quantifiable concentration
- λz : apparent terminal rate constant λz obtained from the slope of the line, fitted by linear least squares regression, through the terminal points of the natural log of the concentration-versus-time plot of these points
- $t_{1/2}$: apparent terminal half-life, calculated from $(\log_e 2)/\lambda z$
- CL: clearance
- V_d: volume of distribution

Plasma naloxone concentrations below the limit of quantification (BLQ) of the assay will be taken as zero for all calculations. All calculations will be made using raw data.

Compartmental Analysis: Naloxone concentration-time data will also be analyzed using compartmental pharmacokinetic modeling (Phoenix Software, Certara, Princeton, NJ). In addition, a nonlinear mixed-effects model will be employed to determine the population pharmacokinetic parameters of interest using NONMEM, a pharmacokinetic software application. Initially, one- and two-compartment pharmacokinetic models with first-order absorption will be explored. Standard diagnostic plots and goodness of fit parameters will be examined at several key stages to guide the choice of the most appropriate structural and statistical components of the model. The final model will be used to simulate naloxone concentrations using varying doses and dosing regimens.

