Version #	Version Date	Significant Changes from Previous Version
01	02/03/2016	Original Protocol Version
02	04/25/2016	Added additional justification for sample size
03	06/28/2016	Change randomization for the first 3 subjects to naloxone
04	01/05/2017	Add 8mg dose of naloxone; change randomization for the first 8 subjects to naloxone
05	01/31/2019	Update study location

Table of Contents

List of Abbreviations	.6
1.0 Study Contact Information	.7
2.0 Introduction / Background and Rationale	.8

Study Summary

Title	Intra-nasal Naloxone for treatment of impaired awareness of hypoglycemia
Short Title	Intra-nasal Naloxone for impaired awareness of hypoglycemia
IRB Number	1603M84961
Study Sponsor	[name]
Phase	1
Principal Investigator	[name]
Study Design	Single center, single-blind, randomized, cross-over
Study Duration	24 months
Study Center(s)	Clinical Research Unit (CRU)
Objectives	Primary Objective: To evaluate intra-nasal Naloxone as a therapy for prevention and treatment of impaired awareness of hypoglycemia.
	Secondary Objective: Characterize naloxone pharmacokinetics following multiple administrations.
Number of Subjects	18
Main Inclusion Criteria	Males and females between the ages of 18-65 years
Study Product, Dose, Route, Regimen	Narcan (naloxone hydrochloride) intranasal spray, 4 mg/nostril repeated 4 times within 8 hours alternating nostrils.
Duration of Administration	4 doses of 4 mg or 2 doses of 8 mg administered over 1 day.
Endpoints	Primary endpoint will be the within person difference in peak epinephrine secretion during the morning episodes of hypoglycemia on days one and two; we will compare this difference between the two treatment conditions.
	Secondary endpoint will be naloxone pharmacokinetics including maximum concentration (Cmax), time to maximum concentration (Tmax) and area under the curve (AUC).
Statistical Methods	We will fit a general linear mixed model with fixed effects for treatment (naloxone vs. placebo), treatment order (naloxone first vs. placebo first), and period (Part 1 vs. Part 2) and a random effect for participant. We will also consider adjustment for important baseline characteristics, such as age and sex. Diagnostics will be examined to assess model assumptions.

List of Abbreviations

AE	Adverse Event	
CFR	Code of Federal Regulations	
CRF	Case Report Form	
DSMB	Data and Safety Monitoring Board	
DSMP	Data and Safety Monitoring Plan	
FDA	Food and Drug Administration	

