6.3 Laboratory Testing Procedures

6.3.1 Frequency of Blood Draws

Three to five milliliter blood samples will be collected for determination of plasma naloxone concentrations prior to dosing, at 5 ± 1 , 15 ± 2 , 30 ± 3 minutes, and at 1.08 ± 5 , 1.5 ± 5 , 2, 3, 4, and 6 hours after completion of the first IN dose. The actual blood collection times for hours 2 through 6 may deviate by ± 10 minutes from the specified times. In all cases, the actual time of the blood draw will be recorded. Missed samples or breakage of a sample will be recorded.

Baseline blood samples will be drawn for glucose, glucagon, epinephrine, norepinephrine and cortisol before the dose of Naloxone or placebo and before the start of the insulin clamp. During the morning study on day 1, blood samples will be collected every 5 minutes for monitoring of blood glucose levels and every 15 minutes during the last 90 minutes of the clamp, for later measurement of serum glucagon, epinephrine, norepinephrine and cortisol. Afternoon clamp on day 1 will proceed as in the morning except that no serum or plasma will be collected except

for the monitoring of glucose and collection of samples for subsequent measurement of naloxone. On day 2 blood samples will be collected as on the morning of day 1.

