6.4 Clinical Procedures

6.4.1 Treatment Regimen

This study will consist of two 2-day intervention visits separated by approximately 8 weeks.

Subjects will be asked to report to the research center by 7 am on the first day of the study after fasting overnight. On arrival, intravenous lines will be placed in each arm (one will be used for infusions and the other for blood sampling). A minimum of 30 minutes after the IVs are placed, baseline blood samples will be drawn for later measurement of glucose, glucagon, epinephrine, norepinephrine, and cortisol. Subjects will then be given a 4 mg (0.1 ml) or 8 mg dose (0.2 mL of IN naloxone or a similar volume of IN placebo.. After naloxone or placebo dose, a hyperinsulinemic (2.0 mu/kg/min) hypoglycemic (target = 50 mg/dl) clamp protocol will be started. The clamp will be maintained for 2 hours. Blood samples will be collected every 5 minutes for monitoring of blood glucose levels and every 15 minutes during the last 90 minutes for later measurement of serum glucagon, epinephrine, norepinephrine and cortisol. If the subject received 4mg dose of IN naloxone or placebo, a second dose of 4 mg IN naloxone or placebo will be given at +30 min after the start of insulin clamp. Every 15 minutes during the last 90 minutes minutes of the morning clamp, subjects will be asked to quantitate their hypoglycemia related symptoms using a standardized questionnaire (12). At the completion of the morning clamp, glucose will be given to return the participant to normal glucose. 2 hours after the end of the morning clamp, a second 2 hour hyperinsulinemic (2.0 mu/kg/min) hypoglycemic (target = 50 mg/dl) clamp protocol will be started. At the start of this afternoon clamp study, a dose of 4 mg or 8 mg of IN naloxone or placebo will be given. Afternoon clamp will proceed as in the morning except that no serum or plasma will be collected except for the monitoring of glucose and collection of samples for subsequent measurement of naloxone. If the subject received 4 mg dose of intra-nasal naloxone or placebo, a second dose of 4 mg intra-nasal naloxone or placebo will be given after 30 minutes. After the completion of the afternoon clamp, subjects will be returned to euglycemia and fed a meal. They will then be allowed to leave the research center with instructions to return the next morning after an overnight fast. At 7 AM on day 2 they will undergo a single 2 hour hyperinsulinemic hypoglycemic clamp (target blood glucose 50 mg/dl) during which blood samples will be collected as on the morning of day 1. Symptom scores will be collected every 15 minutes during the last 90 minutes of the clamp. At the end of the study, infusions will be stopped, and participants will be fed a meal and then sent home after they are scheduled to return for Part 2 in 8 weeks. This timing is selected to ensure that female participants are studied at the same phase of the menstrual cycle; males will return for Part 2 in 8 ± 2 weeks. During Part 2 they will receive the treatment not provided during Part 1. The rest of the study protocol will be the same as in Part 1.

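### Section 6.4.3 takes one Cmax and one Tmax over a day of two to four dosing times, and on the section 6.4.1 schedule the 4 h sample can fall either side of the afternoon dose

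*Combined protocol and SAP*

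**What the plan says.** The Study Summary and section 5.3.2 list Cmax and Tmax among the secondary pharmacokinetic endpoints. Section 6.4.3 defines Cmax as the "maximum observed plasma concentration" and Tmax as the time to reach it, and adds that "T_{max} and C_{max} will be determined from visual inspection of the naloxone concentration-time plots". No section says which doses the maximum covers, which dose Tmax is counted from, or whether 4 mg and 8 mg subjects are summarised separately.

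Section 6.3.1 schedules draws "prior to dosing, at 5 ± 1 , 15 ± 2 , 30 ± 3 minutes", then at 1.08 and 1.5 h, then at "2, 3, 4, and 6 hours after completion of the first IN dose". Nothing is listed between 4 h and 6 h, or after 6 h. "The actual blood collection times for hours 2 through 6 may deviate by" 10 min either way.

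Three places describe the dosing times:
- **Section 6.4.1, text:** the first dose comes before a 2 h clamp, and the 4 mg regimen adds a dose 30 min into it. The afternoon clamp follows 2 h after the morning one ends. "At the start of this afternoon clamp study, a dose of 4 mg or 8 mg of IN naloxone or placebo will be given", again with a further dose 30 min later for the 4 mg regimen.
- **Visit table after section 6.4.1:** two 4 mg doses with the 8 AM clamp and one with the 1 PM clamp.
- **Section 2.0, rationale:** the second 4 mg dose 1 h after the first, and a third about 4 h after the second.

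**The concern.** Cmax and Tmax are easy to interpret after a single dose. Taken over a whole multi-dose day, they depend on which dose the highest drawn sample happens to follow. That can differ between the 4 mg and 8 mg regimens. It can also differ between two subjects on the same regimen whose 4 h samples were both drawn within the permitted window.

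The stakes go beyond a descriptive table. Section 5.1 gives naloxone first to up to 8 subjects, partly to confirm that the intended concentrations are reached, and section 2.0 bases the regimen on matching intravenous concentrations. A peak whose meaning shifts with regimen and draw time is a weak basis for that check.

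**Working it through.** **The plan's own figure.** Section 2.0 says levels stay elevated for about 4 h, or two half-lives: 2 x 2.1 h = 4.2 h, which reproduces. Four hours after a dose, 0.5^(4/2.1) = 27% remains, so an afternoon dose adds to residual morning drug.

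**Where the afternoon dose falls.** With time zero at the first dose and a prompt clamp start:
- Section 6.4.1: 2 h clamp + 2 h gap = 4 h, inside the 4 h sample's window of 3:50 to 4:10. The delay from first dose to clamp start is not stated; beyond about 10 min the overlap disappears.
- Visit table: 8 AM to 1 PM = 5 h. Rationale: 1 h + 4 h = 5 h. Both are about 50 min after the window closes.

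**Model.** One compartment, first-order absorption, doses superposed, concentrations in relative units:

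C(t) = sum over doses of D·ka/(ka − ke)·[exp(−ke·u) − exp(−ka·u)], where u is the time since each dose.

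Here ke = ln 2/2.1 = 0.330 per h, from the plan's half-life. The documents give no absorption rate. I assumed a single-dose Tmax of 0.25, 0.33 and 0.50 h, which gives ka = 15.81, 10.94 and 6.19 per h.

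**The 4 h sample on the section 6.4.1 schedule, just before the dose and 10 min after it**

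| Assumed absorption Tmax | 4 x 4 mg | Ratio | 2 x 8 mg | Ratio |
|---|---|---|---|---|
| 0.25 h | 2.38 to 5.82 | 2.4 | 2.18 to 9.21 | 4.2 |
| 0.33 h | 2.40 to 5.51 | 2.3 | 2.20 to 8.56 | 3.9 |
| 0.50 h | 2.46 to 4.82 | 2.0 | 2.26 to 7.12 | 3.2 |

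**Observed Cmax and Tmax for 2 x 8 mg (0 and 4 h)**

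| Assumed absorption Tmax | 4 h draw before dose | 4 h draw at 4:10 | Rise in Cmax |
|---|---|---|---|
| 0.25 h | 7.37 at 15 min | 9.21 at 250 min | 25% |
| 0.33 h | 7.06 at 15 min | 8.56 at 250 min | 21% |
| 0.50 h | 6.78 at 30 min | 7.12 at 250 min | 5% |

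**Observed Cmax and Tmax for 4 x 4 mg (0, 0.5, 4 and 4.5 h).** The highest listed sample is 6.23, 6.29 and 6.33, always at 65 min and whichever side of the dose the 4 h sample falls. The modelled daily peaks are 8.78, 8.62 and 8.31 at 282-292 min, where nothing is drawn. The ratios are 0.71, 0.73 and 0.76, so observed Cmax is 24-29% below the day's peak.

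**What follows the afternoon dose.** If the 4 h draw precedes the dose, only the 6 h sample remains. It is 66-73% of the modelled peak for 4 x 4 mg (5.83/8.78 to 6.03/8.31) and 57-64% for 2 x 8 mg (5.35/9.38 to 5.53/8.71).

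**Sensitivity to absorption.** At 0.15 h the 4 h ratios are 2.6 (4 mg) and 4.5 (8 mg), and the 2 x 8 mg pattern is the same. With slow absorption it changes. At 0.75 h and 1.0 h the ratios are 1.4-2.4, and the timing of the 4 h draw no longer moves the 2 x 8 mg Tmax (1.08 h and 6.00 h respectively). The 4 x 4 mg Tmax moves to 6.00 h. Across 0.15-1.0 h, the 4 x 4 mg Tmax is either 1.08 h or 6.00 h and never the single-dose value, except that 1.08 h comes close when the assumed value is itself about 1 h.

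**If the afternoon dose is at 5 h.** The 4 h sample changes only by decay (a factor of 0.90 from 3:50 to 4:10). With three 4 mg doses, and absorption at 0.15-1.0 h, observed Tmax is 1.08-1.50 h on the visit table and 1.08-2.00 h on the rationale schedule. An undivided maximum is still unstable if section 6.4.1's dose numbers are put on the 5 h clock. At 0.25-0.50 h, 4 x 4 mg then gives 6.00 h, and 2 x 8 mg gives 0.25 h or 6.00 h depending on absorption.

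**The case against.** The secondary objective is pharmacokinetics after multiple administrations, so a whole-regimen maximum is a legitimate description. Actual draw times (section 6.3.1) and dose times (section 9.3) are recorded, so each 4 h value can later be classed as before or after the dose. Section 6.4.3 also plans compartmental and population models with first-order absorption, which can use those times. The endpoint is secondary and descriptive, with no test between 4 mg and 8 mg. All of this stands and limits the consequence. It does not repair the non-compartmental Cmax and Tmax, which would still be tabulated under a rule that lets them change meaning.

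Three stronger readings are tempting, and the documents do not support them:
- *Tmax merely reports the dosing timetable.* For 2 x 8 mg with the 4 h draw before the dose, observed Tmax is 15-30 min, which reflects first-dose absorption. For 4 x 4 mg, the 282-292 min peak lies on the modelled curve at a time when no sample is taken. Section 6.4.3 uses the observed maximum, so the plan would not report that peak.
- *The 4 h window always straddles the afternoon dose.* That holds only on the section 6.4.1 schedule with a prompt clamp start.
- *The cure is a separate afternoon Cmax and Tmax.* With one sample after the dose, that Tmax would be about 120 min for everyone on the section 6.4.1 schedule, fixed by the sampling grid. Cmax would be 27-43% below the modelled peak.

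Reading Cmax by eye is a small matter, since it is already defined as the observed maximum.

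**Conclusion.** The point holds in limited form. Cmax and Tmax lack a dosing interval and a regimen, and this does not depend on any model. On the section 6.4.1 schedule with a prompt clamp start, two draws that both comply with the window can move the 2 x 8 mg Tmax by nearly 4 h and Cmax by 5-25%, while the 4 x 4 mg Tmax stays at 65 min. Pooled values would therefore not describe one quantity.

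These sizes rest on the plan's half-life of 2.1 h, a one-compartment model and an assumed absorption Tmax of 15-30 min. The shift in the 2 x 8 mg Tmax does not appear if absorption takes 45 min or longer. The overlap itself is clock arithmetic, and disappears if the afternoon dose is near 5 h. The primary endpoint is not affected.

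**What to change.** 1. Reconcile the dosing times and number of doses in section 2.0, the section 6.4.1 text and the visit table. Which schedule applies is for the sponsor to settle.
2. In section 6.3.1, require the 4 h sample to be drawn before the afternoon dose.
3. In sections 5.3.2 and 6.4.3, define the non-compartmental Cmax and Tmax on the morning dosing episode, from the first dose to the last sample before the afternoon dose. Use the highest assayed value and its actual time.
4. Summarise both by regimen. State that the 4 mg morning values follow two doses, so their Tmax is not a single-dose absorption time.
5. Report the 6 h result as a concentration at its actual time after the afternoon dose, not as an afternoon Cmax or Tmax. Take afternoon peak exposure from the planned compartmental and NONMEM analyses, using recorded dose and draw times.

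The cost is slightly more pharmacokinetic wording and the loss of a non-compartmental whole-day or afternoon peak. No extra samples are needed.

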6.5 Follow-Up Procedures and Therapy Transitions

Subjects may contact study personnel after completion of the study with concerns or questions.

6.6 Study Timetable / Schedule of Events

See above section 6.4.1

6.7 Study Protocol Compliance / Treatment Adherence

Safety and tolerability will be evaluated in all subjects who receive study drug whether or not they complete the study. Subjects are required to stay at CRU research facility for 3 hours after the last dose of study drug administration. If they do not complete the study; a new subject will be recruited to ensure a final sample size of 15 completers.

6.8 **Protocol Amendments after Study Initiation**

Should changes in the study plan or protocol become necessary in the course of the clinical trial, those specific changes will be discussed and agreed upon by the Investigators, and appropriate IRB approval obtained before the changes are implemented. All changes must be documented as protocol amendments.

6.9 Deviations from the Clinical Protocol

When a deviation from the protocol is necessary for an individual subject, the investigator must complete a description of the deviation from the protocol and justification on the Protocol Deviation Form.

6.10 Subject Compensation

Subjects will be compensated \$150 for each day of the study. Total compensation will be \$600 if they complete the entire study.

7.0 Data Collection and Analysis

7.1 Subject Population(s) for Analysis

In this study we intend to enroll normal volunteers. Previously our group has had no trouble enrolling volunteers to participate in studies in which they were asked to experience several periods of hypoglycemia. This is a proof of principle study in which the impact of IN naloxone on hypoglycemia induced blunting of the counterregulatory response will be measured. Normal volunteers who participate in this protocol are expected to have the same degree of hypoglycemia induced blunting in their counterregulatory response as patients with type 1 diabetes and normal awareness of hypoglycemia. Therefore, this design will allow us to determine if naloxone works under controlled conditions. If it does, it will provide rationale to use in patient populations in the future.

7.2 Statistical Methods

Our primary outcome is the peak epinephrine response during the third hypoglycemic clamp of each infusion experiment, thus each participant will have two observations: one from their naloxone experiment and one from their placebo experiment. We will fit a general linear mixed model with fixed effects for treatment (Naloxone vs. placebo), treatment order (Naloxone first vs. placebo first), and period (Part 1 vs. Part 2) and a random effect for participant. We are confident that our study design, with a washout period of 8 weeks between Parts 1 and 2, has minimized the possibility of a treatment effect from Part 1 that lingers into Part 2. We will also consider adjustment for important baseline characteristics, such as age and sex. Diagnostics will be examined to assess model assumptions.

8.0 Safety and Adverse Events

8.1 Definitions

Adverse Event (AE)

An adverse event (AE) is any symptom, sign, illness or experience that develops or worsens in severity during the course of the study. Intercurrent illnesses or injuries will be regarded as adverse events. Abnormal results of laboratory or diagnostic procedures are considered to be adverse events if the abnormality:

- Results in study withdrawal
- Is associated with a serious adverse event
- Is associated with clinical signs or symptoms
- Leads to additional treatment or to further diagnostic tests
- Is considered by the Investigator to be of clinical significance.

Adverse Reaction

An adverse reaction is any adverse event caused by a drug. Adverse reactions are a subset of suspected adverse reactions.

Suspected Adverse Reaction

A suspected adverse reaction is an adverse event for which there is a reasonable possibility that the drug caused the adverse event.

Serious Adverse Event (SAE)

A serious adverse event (SAE) is any adverse event that is:

- Fatal
- Life-threatening
- Requires or prolongs a hospital stay
- Results in persistent or significant disability or incapacity

• Results in a congenital anomaly or birth defect

Important medical events are events that may not be immediately life-threatening, but are clearly of major clinical significance, may be SAEs. They may jeopardize the subject, and may require intervention to prevent one or the other serious outcomes noted above.

Attribution

The relationship of the adverse event and the drug or intervention will be classified as follows:

- Unrelated: The AE is clearly NOT related to the intervention
- Unlikely: The AE is doubtfully related to the intervention
- **Possible:** The AE may be related to the intervention
- **Probable:** The AE is likely related to the intervention
- **Definite:** The AE is clearly related to the intervention.

Hospitalization

Hospitalization shall include any initial admission (even if less than 24 hours) to a healthcare facility as a result of a precipitating clinical adverse effect; to include transfer within the hospital to an intensive care unit. Hospitalization or prolongation of hospitalization in the absence of a precipitating, clinical adverse effect (e.g., for a preexisting condition not associated with a new adverse effect or with a worsening of the preexisting condition; admission for a protocol-specified procedure) is not, in itself, a serious adverse effect.

Expected Adverse Event

Expected adverse events are those that are known to be associated with or have the potential to arise as a consequence of participation in the study.

Unexpected Adverse Event

An adverse event or suspected adverse reaction is considered unexpected if it is not listed in the Investigator Brochure or Protocol at the specificity or severity that has been observed.

Unanticipated Problems Involving Risk To Subjects or Others (UPIRTSO)

An adverse event that in the opinion of the Principal Investigator is unexpected, related to the drug, and serious.

